### **7.9.1.5 Analysis Methods**

The proportion of subjects with a reduction in overstimulation sensation during CL compared to the OL period will be calculated and evaluated with a one-sided 97.5% confidence lower bound. This proportion will be tested against 50% using a binomial exact test. The confidence lower bound needs to be greater than 50%, or equivalently, the p-value needs to be less than 0.025 to declare a study success. This implies that among the estimated total 42 randomized subjects, 28 subjects or more need to have a reduction in overstimulation sensation for the study to be considered a success.

Two sensitivity analyses will be performed if there is any missing primary endpoint data. One sensitivity analysis, a tipping point analysis, will be performed using the ITT Analysis Set. This analysis will be performed on the primary endpoint by displaying the full range of proportions on the potential impact of missing data by running an analysis assuming all missing values are a higher average stimulation intensity value for CL vs OL (worst case) to all missing values are a lower average stimulation intensity value for CL vs OL (best case).

Another sensitivity analysis will be performed on the primary endpoint by including only the subjects who finish the in-clinic testing and provided the scoring of overstimulation sensation for both OL and CL periods (Completer Analysis Set).

## 7.10 Safety Evaluation

All serious, device-related, procedure-related and/or therapy-related adverse events (AEs) and all device deficiencies (DDs) will be considered reportable for this study and will be characterized from the start of the in-clinic testing until study exit. AEs and DDs will be coded and summarized using the Medical Dictionary for Regulatory Affairs (MedDRA). Serious AEs will be summarized for all consented subjects (Enrolled Analysis Set), all subjects who are randomized (ITT Analysis Set), as well as for subjects who

provide overstimulation data (Completer Analysis Set). Device-related, procedure-related, and/or therapy-related AEs and DDs will be summarized for all subjects who underwent the OL and/or CL periods during the in-clinic visit (Completer Analysis Set). The severity, treatment needed, resolution, and relevant principal investigator's judgment concerning the causal relationship with the devices or procedure or therapy will be provided as listing. The number of events, the number of subjects who experience an event, and the percentage of subjects who experienced one or more events will be summarized. A listing of deaths and reasons for deaths will be provided if any deaths occur in the study.

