## 4.3 Safety Assessment

All device-related, therapy-related, and procedure-related adverse events and device deficiencies will be characterized from the start of the in-clinic testing until study exit.

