## 5. Investigation Plan

[figure not shown]
This is a prospective, multi-center, randomized, single-blind, cross-over, non-significant risk Investigation Device Exemption (IDE) study. This study will be conducted in the United States with up to 15 sites; each site will contribute up to 10 enrolled subjects. Up to 60 subjects are expected to be enrolled in the study to allow for at least 42 subjects for analysis.

The expected total study duration is approximately 6 months. The duration of a subject's participation is approximately 2 weeks from enrollment, although this may vary depending on when enrollment occurs relative to the SCS device trial.

[Figure 5-1](#) is a flow diagram of how subjects will complete the study. Subjects will be required to come into the clinic for 2 study visits, although they could occur on the same day:

- Enrollment
- In-clinic Testing Visit

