**Figure 5-1: Study Visit Diagram**

Subject randomization will occur after a clear, measurable ECAP [REDACTED]  
[REDACTED] is verified and the algorithm is setup. Subjects will be randomized to the sequence of receiving OL and CL in-clinic testing. Subjects will be blinded to the settings tested. The In-clinic Testing Visit is expected to last up to 3 hours and subjects will be discontinued at the end of the visit.

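### Section 7.10 plans to pool adverse events and device deficiencies over the whole in-clinic visit, without showing whether open loop or closed loop was in use at onset

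*SAP*

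**What the plan says.** SAP section 5 describes the design: "This is a prospective, multi-center, randomized, single-blind, cross-over, non-significant risk Investigation Device Exemption (IDE) study". The text under Figure 5-1 adds that "Subjects will be randomized to the sequence of receiving OL and CL in-clinic testing", after the ECAP has been verified and the algorithm set up. It also says: "The In-clinic Testing Visit is expected to last up to 3 hours and subjects will be discontinued at the end of the visit".

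Section 4.3 gives the safety aim: "All device-related, therapy-related, and procedure-related adverse events and device deficiencies will be characterized from the start of the in-clinic testing until study exit". This is one window, with no phases inside it.

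Section 7.10 sets out the display. Serious AEs are summarized in three analysis sets (Enrolled, ITT, Completer). For related AEs and device deficiencies there is one group: "DDs will be summarized for all subjects who underwent the OL and/or CL periods during the in-clinic visit (Completer Analysis Set"). The statistics are the number of events and then "the number of subjects who experience an event, and the percentage of subjects who experienced one or more events will be summarized". A listing covers severity, treatment needed, resolution and the investigator's view of causality with respect to devices, procedure or therapy. Section 7.7, on treatment characteristics, adds nothing on this point.

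**The concern.** In a parallel-group trial, a table of subjects with events can be split by arm because each subject belongs to one arm. In this crossover each randomized subject is planned to belong to both, so the setting becomes visible only if events are tabulated by what was in use when they began. Section 7.10 does not plan that.

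The primary endpoint is built by period: an average intensity score for OL, another for CL, and a comparison within subject. The safety display has no such structure, although the CL algorithm is what the study evaluates. A reader of the planned tables and listing would not learn whether reportable events or deficiencies gathered under CL, gathered under OL, or fell evenly. For device deficiencies the distinction has its own meaning, since a fault while the algorithm is running and a fault in open loop call for different interpretations.

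**Working it through.** Section 7.10 states no event rate or other figure, so there is nothing of the plan's own to reproduce. The check is a reading of the text, followed by one illustration.

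**Step 1. Does any planned output carry the setting?**

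| Output in SAP 7.10 | What it separates | OL or CL at onset? |
|---|---|---|
| Serious AEs by Enrolled, ITT, Completer | Who is in the denominator | No; the ITT and Completer sets mix both settings, and Enrolled also contains them |
| Related AEs and DDs | One group, having had either or both periods | No |
| Events, subjects, percentage | Counts over the whole window | No |
| Listing | Severity, treatment, resolution, causality | Not named |

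Sections 4.3 and 7.7 supply no split either. Section 7.10 shows no visible redaction, and the tabulation of AEs is SAP content rather than something usually left to the protocol.

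**Step 2. What can the pooled table hide?**

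Inputs: 42 subjects, the number the SAP expects to be randomized (sections 6 and 7.9.1.5). Assume all 42 enter both periods. The four subjects with an event are invented for illustration; the documents give no rate.

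| | Scenario A: all four under CL | Scenario B: two under OL, two others under CL |
|---|---|---|
| Planned row | 4/42 = 9.5% | 4/42 = 9.5% |
| OL at onset | 0/42 = 0.0% | 2/42 = 4.8% |
| CL at onset | 4/42 = 9.5% | 2/42 = 4.8% |

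The planned row is identical in the two scenarios; the rows by setting differ.

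**Step 3. Would a split support a test?**

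In scenario A all four discordant subjects fall on the CL side. The two-sided exact McNemar p-value is 2 × 0.5^4 = 0.125. Even the extreme split of four subjects is not significant at conventional levels, so the table can only be descriptive.

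**Step 4. Which denominator?**

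Section 7.10 labels subjects with either period as the Completer set, whereas section 7.1.3 requires ratings in both periods. A subject who stops in the first period, for instance because of an event, could have no rating for the second and so fall outside the set as defined in 7.1.3. Counting subjects who entered each phase keeps that subject in view whichever reading of the label applies.

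**The case against.** The strongest reply is that this is silence and not error. Section 7.10 does not say that events will be reported without a split, and section 7.11 allows changes that are not principal features to be made and explained in the study report. That stands: a split remains possible. Naming it beforehand is still better than assigning events to settings after the results are known.

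Second, the SAP meets its own safety aim. Section 4.3 promises to characterize events; no visible text promises or powers a safety comparison of OL with CL. This also stands, and it limits the weight of the point. So does the short visit of up to 3 hours, in which few events are likely (an assumption). Moreover, the discomfort most clearly tied to the setting, overstimulation, is already compared within subject as the primary endpoint. Only reportable events beyond it lack a stated split.

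Third, a reader might infer that the crossover is unable to show which setting events belong to, or that the within-subject safety comparison is lost. The documents do not support that. If onset times or periods are recorded, events can still be assigned; the limit lies in the planned outputs. Nor does the pooled table charge CL with events from OL or set-up, since it makes no attribution to CL.

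Fourth, a reader might infer that the causality categories cannot separate the settings because OL and CL share device, procedure and therapy. The SAP does not define those terms, and the protocol may treat the algorithm separately. What can be said is that the listing, as described, does not name the setting.

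Finally, assignment by onset can misplace an event in the second period whose cause lies in the first. That is a real limit of the proposed table, and the reason to show sequence.

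**Conclusion.** The point holds for the outputs as planned: neither the summaries nor the listing in section 7.10 identifies OL or CL at onset, so they do not show under which setting events arose. It is of minor to moderate importance. It affects what the report can say descriptively about the safety of the algorithm under study; it does not affect the primary analysis or its conclusion.

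The documents give no basis for an expected size, and the 4/42 example is hypothetical. The verdict assumes that the case report form records onset time or testing period, which cannot be checked here. The SAP also does not say whether algorithm set-up falls inside a window that opens with the start of in-clinic testing, so whether a set-up row applies is open.

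**What to change.** In section 7.10:

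- Add a descriptive tabulation of AEs and device deficiencies by phase at onset: OL, CL and, where they lie inside the reporting window, set-up and the time after both tests until exit. State whether set-up is inside that window.
- Use the subjects who entered the phase as its denominator. Count a subject once in each phase in which an event began and once in the overall row, so the phase rows need not add up to it.
- Add phase at onset and randomized sequence to the AE and DD listings, so that possible carry-over into the second period can be seen.
- Keep the overall row as planned, and state that no inference between settings is intended.

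The cost is SAP wording, some table columns and two listing fields, with no new study procedure, provided onset time or period is already collected. If it is not, a field on the case report form is needed as well. The remaining downside is that counts will probably be low and should be read as such.

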## **7.11 Changes to Planned Analysis**

Any changes to the data analysis methods described in the SAP will require an amendment only if it changes a principal feature of the SAP. Any other change to the data analysis methods described in the SAP, and the justification for making the change, will be described in the clinical study report.

## **8. Validation Requirements**

Statistical programming code that affects the result of the main analysis for the primary objective shall be validated using Level I validation, which is defined as the peer reviewer independently programs output and then compares the output with that generated by the original Statistical Programmer.

Statistical programming code that affects the result of the main analysis for the additional measures shall be validated using Level II validation, which is defined as the peer reviewer reviews the code; where appropriate, performs manual calculations or simple programming checks to verify the output.

In addition, the main statistical analyses that are planned for publication and have not been previously validated should be validated with at least Level II validation. The CIP deviation summary shall be validated using at least Level III validation and the high-level adverse event summary shall be validated using at least Level II validation. Additional measures where a p-value or confidence interval has been generated may need to be validated using at least Level II validation.

